 - Beginning at Week 2 (based on the Day 1 A4 measurement), subjects with an A4 measurement \leq ULN at a study visit will begin to reduce their daily GC dose in increments of no more than 5 mg/day HCe each time, down to a minimum of 15 mg HCe per day. Beginning at Week 6 (based on Week 6 A4 measurement), subjects with an A4 $>1.25 \times$ ULN will begin to increase their daily GC dose by increments of no more than 5 mg/day HCe each time. More details on GC dose adjustments are provided in [Section 4.1.4.3](#).
 - Subsequent GC dose adjustments are based on A4 measurements at Weeks 12, 18, 24, 32, 40, 52 and 64.
- For subjects continuing into the optional *Open-Label Extension Period*:
 - The Open-Label Extension Period will provide subjects with up to 240 weeks of treatment with tildacerfont 200 mg QD.
 - Subjects will be eligible to adjust GC dose level at each visit (see [Section 4.1.4.3](#)).
- A 30-day *Follow-up Period at EOT*
 - Subjects who do not continue to the Open-Label Extension Period upon completion of Treatment Period will enter a 30-day Follow-up Period.
 - Upon completion of the Open-Label Extension Period, subjects will enter a 30-day Follow-up Period.
 - At the end of study treatment, subjects will maintain the GC regimen and mineralocorticoid regimen (as applicable) established during the course of the study until the 30-day follow-up visit unless the Investigator determines that the subject's clinical status necessitates a dosing change. After completion of the study, GC therapy will be managed at the discretion of the subject's treating physician.

Study Visit Schedule

- During the Screening Period:
 - Optional A4 Screening Visit
 - Screening Visit at \leq 45 days before Day 1

- During the Glucocorticoid Conversion Period (for subjects on dexamethasone at Screening): visits at Weeks -12 and -8 (and -2, if applicable); scheduled telephone contacts at Weeks -11 and -6 (and -5, if applicable)
- During the 24-week Placebo-Controlled Treatment Period: visits on Day 1 (Baseline) and at Weeks 3, 6, 12, 18, and 24
- During the 52-week Open-Label Period: visits at Weeks 32, 40, 52, 64, and 76; scheduled telephone contacts at Weeks 27 and 46
- During the optional Open-Label Extension Period: Visits every 3 to 6 months at Weeks 88, 100, 124, 148, 172, 196, 220, 244, 268, 292 and 316
- At 30 days after the last dose of study drug for final safety follow-up
- As needed (PRN) telephone contacts are detailed under [Telephone Contacts](#)

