⁴ During scheduled telephone contacts, sites will record any AEs and concomitant medications. After receiving A4 results during the Treatment Period, sites will make telephone contacts to applicable subjects regarding GC dose adjustment (detailed later in this Schedule of Activities). Subjects should be instructed to telephone sites if they have any concerns about their health. Telephone contacts initiated by sites and telephone contacts initiated by subjects should be captured in the EDC system as "unscheduled" telephone contacts.

⁵ This visit for safety assessments may be scheduled for any day of Week 3, for any time of day, at the subject's convenience. Clinical laboratory can be measured at any time of day for this visit and need not occur before the morning dose of GC.

⁶ Samples for these lab assessments will be obtained at 8 AM (± 1 hour), after an overnight fast (nothing to eat after midnight) and before any morning dose of GC medication. On the evenings before scheduled laboratory assessments, subjects should take their evening GC dose before 10 PM.

⁷ A4, 17-OHP, ACTH, and testosterone will be measured.

⁸ Clinical laboratory assessments include hematology, clinical chemistry (including liver function tests such as ALT, AST, ALP, GGT, total and direct bilirubin, and total bile acids), coagulation (PT/INR, and PTT), lipid panel, thyroid panel, LH, FSH, SHBG, renin, aldosterone, inhibin B for males only, and estradiol, prolactin, and progesterone for females only.

⁹ A single blood sample will be drawn for PK measurement at each specified visit.

¹⁰ Where local regulations permit and subject to discretionary approval from each site's IRB/EC and to subject consent, a voluntary blood sample may be collected for DNA analysis. See [Section 13.4](#) for specifics on genetic testing that may be performed.

¹¹ Vital signs consist of systolic and diastolic blood pressure, pulse rate, body temperature, and respiration rate and will be measured after a 5-min rest period.

¹² The initial scrotal ultrasound may be scheduled for any time before the first dose of study drug and will be considered the baseline measurement for TART.

¹³ Scrotal ultrasounds will only be conducted in subjects who had TART(s) at baseline.

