Study SPR001-204 will treat subjects with tildacerfont for up to 76 weeks, significantly longer than previous Phase 2 studies. The initial Phase 2 Study SPR001-201 treated subjects with tildacerfont for 2 weeks at each dose level ranging from 200 mg to 1000 mg per day. The subsequent Phase 2 Study SPR001-202 treated subjects with tildacerfont for 12 weeks at 400 mg QD. The magnitude of the efficacy response strengthened over 12 weeks of therapy, suggesting that the full treatment effect of tildacerfont may only be revealed after longer-term therapy. Study SPR001-204 will treat subjects with randomized study drug for 24 weeks during the Placebo-Controlled Treatment Period and with open-label tildacerfont for a further 52 weeks during the Open-Label Period. An optional Open-Label Extension Period will provide up to an additional 240 weeks of open-label treatment with tildacerfont at 200 mg QD. This duration of treatment will provide much longer-term monitoring of clinical outcomes for this chronic drug. The 30-day post-treatment washout period allows for adequate safety follow-up and analysis of any HPA axis rebound after the last dose of study drug.

Subjects cannot be on dexamethasone during this study because dexamethasone may have a moderate drug interaction with tildacerfont that would confound efficacy analysis. Based on nonclinical and Phase 1 clinical data, tildacerfont is a moderate inhibitor of CYP3A4. Dexamethasone is primarily metabolized through CYP3A4, and GC exposure data from Study SPR001-201 have shown a potential for drug-drug interaction (DDI) between tildacerfont and dexamethasone, with tildacerfont increasing dexamethasone exposures approximately 1.8-fold and with the lower bound of the associated 95% confidence intervals (CIs) generally above 1.0. In contrast, prednisone/prednisolone and HC are metabolized through multiple pathways, with CYP3A4 comprising <18% of its metabolism ([Kovacs 2019](#), [Ohno 2008](#)). Based on static mechanistic modeling used to predict DDI ([FDA 2000](#)), no clinically relevant increase in GC exposure is expected with prednisone/prednisolone or HC and tildacerfont. Phase 2 clinical data have shown a low likelihood of a DDI with tildacerfont.

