4.3 Justification for Dose

In Study SPR001-204, tildacerfont tablets will be administered at 200 mg QD for up to 76 weeks. Data from previous Phase 1 and Phase 2 studies support the safety and potential PD effects of this dose.

The safety data show that tildacerfont has been generally well tolerated in all clinical studies to date, with no related SAEs. Specifically, tildacerfont at a dose of ≤ 200 mg/day has been well tolerated in previous clinical studies.

The clinical efficacy/PD data show CRF₁ receptor target engagement (reductions in ACTH) and reductions in key adrenal hormones (17-OHP and A4) in subjects with CAH dosed for 2 weeks with 200 mg/day tildacerfont, the lowest dose previously tested in subjects with CAH (see [Section 2.3.2](#)).

A 1-compartment PK model with first-order absorption and elimination was fit to PK data from Study SPR001-201. This model was then used to estimate the steady-state exposure for each subject at each dose. For each of the 3 key hormones of ACTH, 17-OHP, and A4, an apparent plateau in response is observed at exposures achieved with the 200 mg/day dose of tildacerfont, with no additional benefit at the higher doses. This suggests that a dose of ≤ 200 mg/day tildacerfont may provide maximum benefit while minimizing drug exposure.

The long half-life of tildacerfont, estimated to be approximately 60 hours after single-dose administration, supports QD dosing in this study.

Guided by the safety, efficacy, and exposure-response analyses from available clinical data, Spruce has selected a tildacerfont tablet dose of 200 mg QD for testing in Study SPR001-204. This dose lies within a clinically precedented dose range that has both been well tolerated and produced responses in key hormones.

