6.1.2 Treatment Assignment, Dosing, and Administration

At the beginning of the Placebo-Controlled Treatment Period, subjects will be randomized in a 1:1 ratio to receive either placebo or tildacerfont at 200 mg QD for 24 weeks. During the Open-Label Period, all subjects will receive open-label tildacerfont at 200 mg QD for 52 weeks. During the optional Open-Label Extension Period, subjects will continue to receive tildacerfont at 200 mg QD.

Study drug will be taken orally each day between 6 PM and midnight, with an evening meal. The evening meal should contain approximately 25-50% fat content. Study drug may be consumed up to 30 minutes after completing the evening meal, if necessary.

Subjects entering the study under protocol version 7.0 will use a Principal Investigator-prescribed supply of GCs. Subjects who entered the study under prior protocol versions will continue to use the GCs provided by the Sponsor through Week 24. After Week 24, subjects will use a Principal Investigator-prescribed supply of GCs. Subjects will continue to use the same type of GC (example: switch between short-acting GC and intermediate acting GC shall not be allowed) throughout the study. Please see important details on GC use in Section 4.1.4.1.

On the evenings before scheduled laboratory assessments, subjects should take their evening GC dose before 10 PM. On the mornings of scheduled laboratory assessments, subjects should delay taking any morning dose of GC medication until after the 8 AM (± 1 hour) laboratory assessments have been completed. On all other days during the study, subjects should take their GC medication at the usual times. Mineralocorticoid may be taken at any time of day, but its timing relative to laboratory assessments should be consistent throughout the study.

Only authorized study staff may dispense study treatment. Sites will provide subjects with dosing instructions. The Sponsor will provide GC for periods of stress dosing. Sponsor-provided HC for stress dosing may be shipped directly to subjects.

In Denmark, UK, Ireland, Romania, Estonia or Turkey shipping of study drug directly from clinic to subject's home is not permitted

Criteria for study drug discontinuation are provided in [Section 7.1](#).

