⁸ Bottles of HC for stress dosing will be dispensed starting at the beginning of the Glucocorticoid Conversion Period and thereafter as needed to replace opened bottles. Accountability for bottles of HC will be performed at every study visit.

⁹ Subjects will use an electronic study diary to document background GC adherence. Female subjects will also use the study diary to record menstrual information (including start and stop dates of menses).

Table 3 Study SPR001-204 Protocol Schedule of Treatment Period and Follow-up Activities

STUDY VISIT NUMBER	Treatment Period												Follow-up ¹	ET
	Placebo-Controlled Treatment Period						Open-Label Period							
5 Base line	6	7	8	9	10		11	12		13	14	15	16	
STUDY WEEK	0	3	6	12	18	24	27	32	40	46	52	64	76	80
STUDY DAY ²	1	22	43	85	127	169	190	225	281	323	365	449	533	Last dose +30 days
Study Visit (V) / Telephone Contact (T) ³	V	V ⁴	V	V	V	V	T	V	V	T	V	V	V	V
Urine pregnancy test for FCP	X		X	X	X			X	X		X	X	X	X
Hormones from blood ^{5,6}	X		X	X	X			X	X		X	X	X	X
Clinical laboratory ^{5,7}	X	X	X	X	X			X	X		X	X	X	X
Urinalysis ⁵	X					X					X		X	X
HbA1c, fasting glucose and insulin, HOMA-IR ⁵	X					X					X		X	X

¹ Subjects who do not continue to the optional Open-Label Extension Period upon completion of the Treatment Period will enter a 30-day Follow-up Period.

² All study visits and telephone contacts should be performed on the indicated study days. In cases where adherence to the foregoing schedule is not possible, all activities for study visits and telephone contacts must be completed within a +6-day window after the indicated study days. The day of the baseline visit (and first dose of study drug) will be considered Day 1 (Week 0), and all other study days are counted relative to Day 1. There is no Day 0 (ie, study days go directly from Day -1 to Day 1).

³ During scheduled telephone contacts, sites will record any AEs and concomitant medications. After receiving A4 results during the Treatment Period, sites will make telephone contacts to applicable subjects regarding GC dose adjustment (detailed later in this Schedule of Activities). Subjects should be instructed to telephone sites if they have any concerns about their health. Telephone contacts initiated by sites and telephone contacts initiated by subjects should be captured in the EDC system as “unscheduled” telephone contacts.

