8.4 Analysis Windows

Clinical visits may occur outside protocol-specified windows. Therefore, instead of relying solely on visit labels in the clinical database, analysis visits and their windows are defined using Enrollment Day or Study Day. For the purposes of data analysis and summary, assessments and/or measurements will be flagged based on the collection date/time that is closest to the protocol-scheduled time point (or Target Study Day). Analysis visit windows are presented in by type of assessments and/or measurements.

Table 12 Visit Analysis Windows (Clinic visits only)

Protocol Specified Visit Number	Analysis Visit	Reference Study Day	Target Study Day	Start (days)	Stop (days)
Visit 1 (Screening)	Screening	Enrollment Day	-114	low	-7
Visit 2	Week -12	Enrollment Day	-84	-6	15
Visit 3	Week -8	Enrollment Day	-56	16	50
Visit 4	Week -2	Enrollment Day	-14	51	high
Visit 5	Day 1	Study Day	1	-6	7
Visit 6	Week 3	Study Day	22	8	32
Visit 7	Week 6	Study Day	43	33	64
Visit 8	Week 12	Study Day	85	65	106
Visit 9	Week 18	Study Day	127	107	148
Visit 10	Week 24	Study Day	169	149	197
Visit 11	Week 32	Study Day	225	198	253
Visit 12	Week 40	Study Day	281	254	323
Visit 13	Week 52	Study Day	366	324	408
Visit 14	Week 64	Study Day	450	409	492
Visit 15 or Extension Visit 1	Week 76	Study Day	534	493	high or 575
Extension Visit 2	Week 88	Study Day	617	576	659
Extension Visit 3	Week 100	Study Day	701	660	785
Extension Visit 4	Week 124	Study Day	869	786	953
Extension Visit 5	Week 148	Study Day	1037	954	1121
Extension Visit 6	Week 172	Study Day	1205	1122	1289
Extension Visit 7	Week 196	Study Day	1373	1290	1457
Extension Visit 8	Week 220	Study Day	1541	1458	1625
Extension Visit 9	Week 244	Study Day	1709	1626	1793
Extension Visit 10	Week 268	Study Day	1877	1794	1961
Extension Visit 11	Week 292	Study Day	2046	1962	2129
Extension Visit 12	Week 316	Study Day	2213	2130	2228
Visit 16 or Extension Visit 13 (follow up)	Follow-up	Study Day		Last dose +1	Last dose +30

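### SAP Table 12 closes the Follow-up window on the visit's scheduled day and lets it overlap Week 76, so a late or missed follow-up visit can put the wrong record in either by-visit summary

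*SAP*

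**What the plan says.** The protocol places the final visit as follows: "At 30 days after the last dose of study drug for final safety follow-up" (Synopsis; the Section 1.3.4 schedule agrees). Protocol Section 4.2 gives its purpose: "The 30-day post-treatment washout period allows for adequate safety follow-up and analysis of any HPA axis rebound after the last dose of study drug".

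SAP Section 8.4 assigns records by date rather than by visit label alone. Its selection rule is that "assessments and/or measurements will be flagged based on the collection date/time that is closest to the protocol-scheduled time point (or Target Study Day"). In Table 12 the Follow-up row, which covers Visit 16 and Extension Visit 13, has a blank target day and the limits "Last dose +1 Last dose +30". The Week 76 row has target Day 534 and starts on Day 493. It stops at *high* for subjects not in the extension and at Day 575 for those who are. There is no early-termination row, and nothing says which window wins when a record fits two.

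On lateness, SAP Table 3, footnote 2, says that visits "must be completed within a +6-day window after the indicated study days". The corresponding footnote to Protocol Section 1.3.4 is garbled in the text available and could be read as ±3 days, as +6 days or as a mixture. Protocol Section 4.1.4.4 defers laboratory draws until 5 to 7 days after a subject returns from stress dosing, and does not count that delay as a deviation. For the extension, SAP Table 4, footnote 1, allows +30 days.

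**The concern.** A window that ends on the scheduled day has no room for lateness, although the plan permits lateness and in places requires it. A window that starts the day after the last dose has no room for washout.

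The two faults compound. When the real follow-up record is pushed out at the top of the window, a record made at the end of treatment can be the only one left inside it. The open-ended Week 76 window then takes in the displaced washout record.

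At stake are the by-visit Follow-up and Week 76 summaries. SAP Section 12.2 includes Follow-up in the Final Analysis. Hormones (SAP 4.3.1.1), ECG (4.3.2.4), clinical laboratory tests (4.3.2.5) and PK samples (4.3.3) are all planned at that visit, and laboratory and ECG results are summarised by scheduled time point (SAP 13.2 and 13.4). The SAP puts PK analysis outside its scope, so PK is affected only if that analysis reuses these windows.

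**Working it through.** **Inputs.** Follow-up window and selection rule: SAP Table 12 and Section 8.4. Scheduled time, last dose +30: protocol Synopsis. Dosing time: "Study drug will be taken orally each day between 6 PM and midnight, with an evening meal" (Protocol 6.1.2). Sampling time: "Samples for these lab assessments will be obtained at 8 AM" (Protocol 1.3.4; the allowance is ±1 hour). Half-life: "estimated to be approximately 60 hours after single-dose administration" (Protocol 4.3).

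**Anchor day.** Week *w* falls on Day 7*w* + 1, so Week 76 is 7 × 76 + 1 = Day 533. This reproduces the protocol schedule; Table 12 shows 534, one day off. No study drug is dispensed at Week 76 in the main-study schedule. I therefore assume that a subject not entering the extension takes the last dose on the evening of Day 532. The Follow-up window is then Days 533 to 562, and the Week 76 visit falls on its first day.

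**Assignment.** Taking last dose +30 as the Follow-up time point and applying the closest-date rule:

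| Actual follow-up visit | Windows it fits | Record used as Follow-up | Record used as Week 76 |
|---|---|---|---|
| +25 (Day 557) | Week 76 and Follow-up | Day 557 | Day 533 |
| +30 (Day 562) | Week 76 and Follow-up | Day 562 | Day 533 |
| +31 (Day 563) | Week 76 only | Day 533 | Day 533 |
| +36 (Day 568) | Week 76 only | Day 533 | Day 533 |
| +30, Week 76 missed | Week 76 and Follow-up | Day 562 | Day 562 |
| +31, Week 76 missed | Week 76 only | none | Day 563 |

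If the follow-up visit never takes place, Day 533 is again the only Follow-up candidate.

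**Permitted days inside the window.**
- Read as 0 to +6 (days +30 to +36): 1 of 7.
- Read as ±3 (days +27 to +33): 4 of 7.
- Read as −3 to +6 (days +27 to +36): 4 of 10.

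Under every reading, all late days are outside.

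**Exposure.** The fraction remaining is 0.5^(t/60 h).
- 8 to 14 h (midnight or 6 PM to 8 AM): 0.91 to 0.85.
- 3 days (72 h): 0.44.
- 7 days (168 h): 0.14.
- 12.5 days (five half-lives): 0.03.
- 30 days (720 h, 12 half-lives): 0.0002.

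The window therefore spans near-full exposure to essentially none. An early-termination record is close to on-drug only when it is made within a few days of stopping.

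**Extension.** With the last dose on Day 2212, the Follow-up window is Days 2213 to 2242. A +30-day allowance permits Days 2242 to 2272, so 1 of 31 permitted days is inside. The Week 316 window stops on Day 2228, so a late record there falls in no window.

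**Early stoppers.** A subject who stops drug on Days 139 to 168 and stays in the study has the Day 169 visit inside both the Week 24 and the Follow-up windows, because 169 − 30 = 139.

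**The case against.** The strongest reply is that the harm is conditional and bounded. Most of it stands.

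- **Selection rule.** The blank target cell does not leave the rule without an anchor, because the protocol's scheduled time is last dose +30. A follow-up visit on or shortly before that day beats a record from last dose +1. A reader might infer that the Follow-up summary would generally consist of on-drug values. The table above shows that this needs a late or missing visit.
- **Late main-study records.** They are not left without a window: they fall into the open-ended Week 76 window and, when Week 76 was attended, lose to it there.
- **Last dose on Day 532.** This is an inference. If the last dose is taken on the evening of Week 76 itself, that visit is on last dose +0 and outside Follow-up. A late follow-up visit then leaves the Follow-up slot empty rather than wrongly filled.
- **Visit labels.** Section 8.4 says only that labels are not the sole basis, so a programmer might use them sensibly. But no rule says how.
- **Masking of unresolved abnormalities.** A reader might infer that a liver or ECG abnormality that fails to resolve would be hidden. The documents do not support that. All laboratory and ECG results are listed (SAP 13.2, 13.4). Clinically significant laboratory values are repeated at least weekly (Protocol 8.2.5), and liver events are monitored until they resolve, stabilise or return to baseline (Protocol 13.2.1.3). Adverse events are classified by onset date (SAP 8.3.22).
- **Endpoints.** No efficacy endpoint analysed under this SAP is measured at Follow-up.

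What does not stand is the suggestion that this is merely missing detail. The stated limits, applied as written, give a wrong by-visit result for a visit that may be only one day late.

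**Conclusion.** The point holds in this conditional form. Table 12 excludes every late follow-up visit and, for main-study subjects, sends the washout record to Week 76. The remaining Follow-up candidate can be the Week 76 record, or an early-termination record made soon after stopping. If Week 76 was missed, the washout record stands in for it.

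The size per affected subject is large: about 85% to 91% of drug remaining against 0.02% at 30 days, assuming first-order decay, the single-dose half-life and a last dose on the evening before Week 76. The number of affected subjects cannot be derived, because the documents give no rate of late or missed visits. The share of permitted days in window is 1 of 7 if the SAP's +6-day copy governs, and up to 4 of 7 under ±3 days.

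The consequence is confined to by-visit Follow-up and Week 76 summaries. It matters mainly for the rebound question that the washout period is meant to address.

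**What to change.** Amend SAP Table 12 and add a short precedence rule:

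1. Set the Follow-up target to last dose +30.
2. Start the window well after the last dose, for example at +14, which is past five half-lives (12.5 days). Stop it late enough for the permitted lateness: at least +36 in the main study, and +60 for Extension Visit 13 if the +30-day allowance applies. The separate extension SAP should use the same row.
3. For subjects not entering the extension, end the Week 76 window before the Follow-up window starts. With a +14 start, that is last dose +13 for those treated through Week 76. For subjects who stopped drug earlier but stayed in the study, the label rule below decides.
4. State that a scheduled treatment-period or early-termination visit keeps its own label and is never used as Follow-up, whatever the interval since the last dose. State also that a record collected as Visit 16 or Extension Visit 13 is never used as Week 76.

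The label rule is needed as well as the new limits. A subject who stops drug and remains in the study can have a scheduled visit well inside any reasonable Follow-up window. The main-study visit allowance should also be confirmed, since the protocol footnote is unclear.

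The cost is two table rows and a few sentences, with no new data. The downside is that a follow-up visit made before the start day is listed but not summarised as Follow-up.
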